#### **4.5. Dose Justification**

GSK2646264 will be administered topically as a cream at 1% (w/w) strength. The maximum topically applied dose to any subject at any time point will be 10mg/cm^2 of cream over 90 cm^2 (maximum of ~0.5% Body Surface Area as determined by [Du Bois, 1916](#)). This equates to a maximum of 900mg of cream and therefore 9 mg of GSK2646264. A corresponding placebo will also be applied. Cream will be weighed both before and after application.

In part A of the first time in human study in healthy subjects (study 200196, NCT02424799, GlaxoSmithKline Document Number [2013N167482](#)) GSK2646264 was given for up to 4 days as a cream of 1% strength (w/w) covering 5.2% BSA for 2 days followed by 10.2% BSA for 2 days. Preliminary data from the FTIH study suggests that GSK2646264 penetrates through the skin and reaches the systemic circulation.

A Population pharmacokinetics model was developed using clinical data from study 200196 part A (N=17 healthy volunteers) and 3 cold urticaria subjects from part B. This model predicted, for GSK2646264 administered topically as a cream of 1% strength (w/w) on 0.5% of BSA, a Cmax of 0.780 ng/mL and an AUC (0-24) at steady state of

17.2. ng.h/mL. Those exposures are well within safety margins as described in the Investigator Brochure and supplement [GlaxoSmithKline Document Number [2013N182566\\_02](#), GlaxoSmithKline Document Number [2015N268236\\_01](#) (Supplement 1) and GlaxoSmithKline Document Number [2016N281634\\_00](#) (Supplement 2)]

Preclinically, when GSK2646264 was administered into *ex-vivo* human healthy skin *via* a microdialysis tube a dose-dependent inhibition of IgE-stimulated histamine release from dermal mast cells was observed. The concentration of GSK2646264 required to inhibit 90% histamine release in anti IgE-stimulated skin *ex vivo* is achievable by the topical route when administered at the 1% strength see GSK2646264 Investigator Brochure.

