11.2. Appendix 2: Data Display Standards & Handling Conventions

11.2.1. Study Treatment & Sub-group Display Descriptors

Study population and Safety displays will be presented by sequence. Treatment will not be used to summarise these endpoints as all subjects will receive both active and placebo concurrently.

Study Group Descriptions			
RandAll NG		Data Displays for Reporting	
Strata Code	Description	Description	Order [1]
A	Group A - Fewer than 2 active lesions (PV)	Group A - (PV lesions)	1
B	Group B - At least 2 active CLE lesions	Group B – (CLE lesions)	2

Group A sequence descriptions:

Sequence Descriptions			
RandAll NG		Data Displays for Reporting	
Code	Description	Description	Order [1]
AA/PC/AD	GSK2646264 skin site A/ Placebo skin site C/ GSK2646264 skin site D	GSK2646264 skin area A/ Placebo skin area C/ GSK2646264 skin area D	1
AA/PC/PD	GSK2646264 skin site A/ Placebo skin site C/ Placebo skin site D	GSK2646264 skin area A/ Placebo skin area C/ Placebo skin area D	2
PA/AC/AD	Placebo skin site A/ GSK2646264 skin site C/ GSK2646264 skin site D	Placebo skin area A/ GSK2646264 skin area C/ GSK2646264 skin area D	3
PA/AC/PD	Placebo skin site A / GSK2646264 skin site C/ Placebo skin site D	Placebo skin area A/ GSK2646264 skin area C/ Placebo skin area D	4

NOTES:

1. Order represents treatments being presented in TFL, as appropriate.
2. Present code as well as description in displays

Group B sequence descriptions:

Sequence Group Descriptions			
RandAll NG		Data Displays for Reporting	
Code	Description	Description	Order ^[1]
AF/PG	GSK2646264 skin site F/ Placebo skin site G	GSK2646264 skin area F/ Placebo skin area G	1
PF/AG	Placebo skin site F/ GSK2646264 skin site G	Placebo skin area F/ GSK2646264 skin area G	2

NOTES:

1. Order represents treatments being presented in TFL, as appropriate.
2. Present code as well as description in displays.

Based on the randomisation schedule, treatments/descriptions will be programmatically assigned to each skin site area. Local tolerability, Efficacy and Pharmacodynamic endpoints are measured at a skin site level and therefore the following treatments will be used:

Group A

Treatment group descriptions			
Skin area		Data Displays for Reporting	
Code	Type	Description	Order
A	PV lesion	GSK2646264 or Placebo ^[2]	1 or 2
B	PV lesion	Baseline lesion	3
C	PV lesion	GSK2646264 or Placebo ^[2]	1 or 2
D	Uninvolved Skin	GSK2646264 or Placebo ^[2]	1 or 2
E	Uninvolved Skin	Uninvolved skin	4

NOTES:

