11.3.2. Study Population

Demographics
Age

 GSK standard IDSL algorithms will be used for calculating age where birth date will be imputed as follows: 
 Any subject with a missing day will have this imputed as day '15'. Any subject with a missing date and month will have this imputed as '30th June'. Birth date will be presented in listings as 'YYYY'.
Body Mass Index (BMI)

 Calculated as Weight (kg) / Height (m)²

Extent of Exposure

 Number of days of exposure to study cream will be calculated based on the formula: Duration of Exposure in Days = Treatment Stop Date – (Treatment Start Date) + 1 Subjects who were randomised but did not report a treatment start date will be categorised as having zero days of exposure. Exposure data on a day is recorded in the eCRF in the following manner: 
 Weight of container and ancillary kit BEFORE application (A) Weight of container and ancillary kit AFTER application (B) Location of cream application, where all locations that apply are ticked (C) 
This means that the weight of cream that was applied on that day (calculated as B-A) is the total dose of cream, with part of the total dose of cream applied to each of all the body locations (C) that are ticked.
 The cumulative dose of cream will be based on the formula:

Extent of Exposure

Cumulative Dose = Sum of (Number of Days x Total Daily Dose of cream)

- If there are any treatment breaks during the study, exposure data will be adjusted accordingly.

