11.8.4. Study Population Tables

Study Population Tables					
No.	Population	IDSL / TST ID / Example Shell	Title	Programming Notes	Deliverable [Priority]
Subject Disposition					
1.1.	Safety	CP_ES1p	Summary of Subject Disposition (Group B-Natural Lesions)		SAC
1.2.	All Screened	ES6	Summary of Reasons for Screen Failure (Group A- PV lesions)		SAC
1.3.	All Screened	ES6	Summary of Reasons for Screen Failure (Group B-Natural Lesions)		SAC
1.4.	Safety	NS1	Summary of Number of Subjects by Country and Centre (Group B-Natural Lesions)		SAC
Protocol Deviation					
1.5.	Safety	DV1	Summary of Important Protocol Deviations (Group B-Natural Lesions)		SAC
Population Analysed					
1.6.	All Screened	SP1	Summary of Study Populations and Exclusions (Group A- PV lesions)		SAC
1.7.	All Screened	SP1	Summary of Study Populations and Exclusions (Group B-Natural Lesions)		SAC

Study Population Tables					
No.	Population	IDSL / TST ID / Example Shell	Title	Programming Notes	Deliverable [Priority]
Demographic and Baseline Characteristics					
1.8.	Safety	DM3	Summary of Demographic Characteristics (Group B-Natural Lesions)	Include BMI	SAC
1.9.	Safety	DM5	Summary of Race and Racial Combinations (Group B-Natural Lesions)		SAC
1.10.	Safety	DM6	Summary of Race and Racial Combination Details (Group B-Natural Lesions)		SAC
Prior and Concomitant medications					
1.11.	Safety	MH1, MH4	Summary of [Current/Past] Medical Conditions (Group B-Natural Lesions)		SAC
1.12.	Safety	CM1	Summary of Concomitant Medications (Group B-Natural Lesions)		SAC
1.13.	Safety	SAFE_T3	Summary of Type of CLE (Group B-Natural Lesions)	Obtained from medical conditions page in eCRF. Under Disease Diagnosis – 2. Disease characteristics.	SAC
Exposure and Treatment Compliance					
1.14.	Safety	EX1	Summary of Weight of Study Cream Applied (Group B-Natural Lesions)	See Section 11.3.2 regarding total daily dose of cream; label first row as "Daily Weight of Cream (g)" with following footnote: "Note: Daily Dose refers to the one lesion that either active or placebo treatment is applied to; Label second row as "Cumulative Weight of Cream (g)".	SAC

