11.8.8. Pharmacokinetic Tables

Pharmacokinetic : Tables					
No.	Population	IDSL / TST ID / Example Shell	Title	Programming Notes	Deliverable [Priority]
4.1.	PK	PKPT1	Summary of Serum GSK2646264 Pharmacokinetic concentrations versus time by actual dose (Group B-Natural Lesions)		SAC
4.2.	PK	PKPT1	Summary of Derived Serum GSK2646264 Pharmacokinetic Parameters by actual dose (Group B-Natural Lesions)		SAC
4.3.	PK	PKPT1	Summary of Log-Transformed Derived Serum GSK2646264 Pharmacokinetic Parameters by actual dose (Group B-Natural Lesions)		SAC

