11.8.12. ICH Listings

ICH : Listings					
No.	Population	IDSL / TST ID / Example Shell	Title	Programming Notes	Deliverable [Priority]
Subject Disposition					
1.	PV Failures	ES7	Listing of Reasons for Screen Failure (Group A- PV lesions)		SAC
2.	All Screened	ES7	Listing of Reasons for Screen Failure (Group B-Natural Lesions)		SAC
3.	Safety	ES2	Listing of Reasons for Study Withdrawal (Group B-Natural Lesions)		SAC
4.	Safety	BL1 / BL2	Listing of Subjects for Whom the Treatment Blind was Broken (Group B-Natural Lesions)		SAC
5.	Safety	CP_RD1x	Listing of Planned and Actual Treatments (Group B-Natural Lesions)		SAC
Protocol Deviations					
6.	Safety	DV2	Listing of Important Protocol Deviations (Group B-Natural Lesions)		SAC
7.	Safety	IE3	Listing of Subjects with Inclusion/Exclusion Criteria Deviations (Group B-Natural Lesions)		SAC
Populations Analysed					
8.	All Screened	SA3a	Listing of Subjects Excluded from Any Population (Group B-Natural Lesions)		SAC
Demographic and Baseline Characteristics					
9.	Safety	DM2	Listing of Demographic Characteristics (Group B-Natural Lesions)	Include BMI	SAC
10.	Safety	DM9	Listing of Race (Group B-Natural Lesions)		SAC

ICH : Listings					
No.	Population	IDSL / TST ID / Example Shell	Title	Programming Notes	Deliverable [Priority]
Medical History					
11.	Safety	MH2	Listing of Medical History (Group B-Natural Lesions)		SAC
Prior and Concomitant Medications					
12.	Safety	CP_CM3	Listing of Concomitant Medications (Group B-Natural Lesions)		SAC
Exposure and Treatment Compliance					
13.	Safety	EX3	Listing of Weight of Study Cream Applied (Group B-Natural Lesions)	If applicable adapt to study data See Section 11.3.2 regarding total daily dose of cream i.e. each subject to have one row per day, with weight of cream listed (the total weight calculated from the weight before and after application), column labelled as "Weight of Cream (g)" and each body location/side listed together on that single row.	SAC
Adverse Events					
14.	Safety	CP_AE8	Listing of All Adverse Events (Group B-Natural Lesions)	No treatment heading.	SAC
15.	PV failures	CP_AE8	Listing of All Adverse Events for subjects that were PV failures (Group A-PV Lesions)	No treatment heading.	SAC
16.	Safety	AE7	Listing of Subject Numbers for Individual Adverse Events (Group B-Natural Lesions)	Treatment column will not be displayed.	SAC

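### The SAP derives one daily cream weight over all treated locations but footnotes it as a one-lesion dose, and no planned display gives the amount of active cream or GSK2646264 applied

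*SAP*

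**What the plan says.** Group B subjects have active cream on one lesion and placebo on the other, once daily for 28 days (Protocol 4.1). No subject was randomised in Group A (SAP 2.1), so exposure reporting concerns Group B only.

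- **Protocol 4.5** sets the ceiling: "The maximum topically applied dose to any subject at any time point will be 10mg/cm 2 of cream over 90 cm 2". It continues: "This equates to a maximum of 900mg of cream and therefore 9 mg of GSK2646264". Placebo comes on top: "A corresponding placebo will also be applied. Cream will be weighed both before and after application".
- **SAP 11.3.2** records a weight of container and kit before and after application, and the locations treated. It says that the weight applied that day "is the total dose of cream, with part of the total dose of cream applied to each of all the body locations" ticked. It derives nothing per site or per treatment.
- **SAP 11.8.12, Listing 13** asks for "each subject to have one row per day, with weight of cream listed", with all locations on that row.
- **SAP 11.8.4, Table 1.14** refers to 11.3.2 for the total daily dose, then requires this footnote: "Daily Dose refers to the one lesion that either active or placebo treatment is applied to".
- **SAP 11.2.1** presents study population and safety displays by sequence: "Treatment will not be used to summarise these endpoints as all subjects will receive both active and placebo concurrently". The same section assigns treatment to each skin site from the randomisation schedule for local tolerability, efficacy and pharmacodynamic displays.
- **SAP 11.8.8** titles all three PK tables by actual dose; Table 4.1, for example, summarises "Pharmacokinetic concentrations versus time by actual dose". The term is not defined.

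**The concern.** Two instructions for one table conflict. A programmer who follows 11.3.2 prints a two-lesion weight; the footnote tells the reader that it is a one-lesion dose. If the footnote is right instead, 11.3.2 and Listing 13 describe the data wrongly.

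Even with the conflict resolved, the plan leaves out the quantity a reader most needs. The primary objective is the safety of the active cream. The protocol's maximum is stated for GSK2646264, and Protocol 6.6 treats any GSK2646264 dose above the intended one as an overdose. No table or listing converts cream weight into active cream or mg of drug. Local tolerability is shown by treatment; exposure is not.

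Lesion size adds to this. F is by definition the larger lesion (Protocol 6.1), so active cream goes on the larger lesion in one sequence and on the smaller in the other. An equal split of a combined weight cannot be taken for granted.

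**Working it through.** **1. Reproduce the protocol's maximum.** Inputs from Protocol 4.5: 10 mg/cm², 90 cm², 1% w/w.

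- Cream: 10 × 90 = 900 mg.
- Drug: 900 × 0.01 = 9 mg.

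Both match the protocol.

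**2. Set the rules side by side.**

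| Place | Meaning of the daily weight | Split by treatment? |
|---|---|---|
| SAP 11.3.2 | Total over all ticked locations | No |
| Listing 13 | One weight per subject per day, all locations together | No |
| Table 1.14 footnote | One lesion, given either active or placebo | Not identified |
| SAP 11.2.1 | Study population displays by sequence | Excluded |

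The first two rows agree with each other and contradict the third. None gives an active weight.

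**3. Size of the mislabelling.** Let the larger lesion F receive r times as much cream as G. A combined weight W read as a one-lesion dose overstates F by W ÷ [W × r/(1+r)] = (1+r)/r, and G by 1+r. The documents give no size ratio, so r is an assumption, with cream taken as proportional to area.

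| r (F:G) | Overstatement for F | Overstatement for G |
|---|---|---|
| 1 | 2-fold | 2-fold |
| 2 | 1.5-fold | 3-fold |
| 4 | 1.25-fold | 5-fold |

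**4. What a combined weight says about the drug.** With W known and the split unknown, the drug applied lies between 0 and 0.01 × W mg.

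| W (mg) | GSK2646264 (mg) | Was the 900 mg / 9 mg active maximum met? |
|---|---|---|
| 900 or less | 0 to at most 9 | Yes, certainly |
| 1200 | 0 to 12 | Cannot tell |
| 1500 | 0 to 15 | Cannot tell |
| 1800 | 0 to 18 | Cannot tell |
| 2000 | 0 to 20 | At least one lesion received over 900 mg, not necessarily the active one |

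As an illustration only, 1500 mg fits 750 + 750 mg (7.5 mg drug) and also 1200 mg active + 300 mg placebo (12 mg; 12 ÷ 9 = 1.33 times the maximum). The documents give no basis for saying which split is likely.

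**5. Dependence on sequence.** Under the assumption in step 3, W = 900 mg corresponds to:

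- r = 1: 4.5 mg of drug in either sequence.
- r = 2: 9 × 2/3 = 6.0 mg when F is active, 9 × 1/3 = 3.0 mg when G is active.
- r = 4: 9 × 0.8 = 7.2 mg and 9 × 0.2 = 1.8 mg.

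Showing Table 1.14 by sequence separates these subjects, but does not recover the split.

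These steps use the size of the weight difference. SAP 11.3.2 writes it as after minus before, which gives a negative number; that is a separate matter.

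**The case against.** The best reply is that nothing shows the data to be pooled. SAP 11.3.2 speaks of a container in the singular, and Protocol section 6 lists active and placebo as separate products in jars. A weight per container, and so per treatment, is a plausible reading, and the Table 1.14 footnote may be the correct text. The Listing 13 note also allows adaptation to the study data, and the eCRF is not among the documents. This stands: a defect in the data is not established, only a conflict in the derivation and displays.

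A reader might also infer more than the documents support:

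- **That the drug maximum cannot be checked at all.** It can whenever the combined weight is 900 mg or less. Deviations are also tracked and listed separately (SAP 4.1).
- **That the PK analysis is blocked.** SAP Table 8 plans AUC, %AUCex, Cmax, tmax and half-life. None uses the applied dose, and only one active strength is studied. The undefined term affects table titles and grouping.
- **That exposure is the denominator for adverse events.** The planned tables do not divide events by cream weight, and days of exposure are derived separately.
- **That every subject and day is affected to a known extent.** Without a lesion size ratio, only a range can be given.

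What the reply does not remove is the contradiction. The Table 1.14 note points to the 11.3.2 total and calls it a one-lesion dose. Even the per-lesion reading leaves active and placebo unidentified.

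**Conclusion.** The point holds as an internal contradiction with a reporting consequence. If 11.3.2 is followed, Table 1.14 misstates the per-lesion dose: twofold at equal amounts, and between 1.25-fold and 5-fold across assumed F:G ratios of 1 to 4. Under either reading, no planned display reports active cream weight or mg of GSK2646264, and the actual dose in Tables 4.1 to 4.3 has no definition. The check against the protocol maximum is conclusive up to a combined 900 mg and open above that.

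This rests on the derivation and display text alone. The documents do not show whether separate weights were recorded, so they do not support saying that active exposure is unrecoverable or that any application exceeded the maximum. In a trial whose primary objective is safety of the active cream, the texts should be reconciled before the exposure tables are programmed.

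**What to change.** State in SAP 11.3.2 whether the eCRF weight is per container or skin site, or a single combined weight. Then take one of two routes.

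- **Weights exist per container or site.** Derive the applied weight for F and G separately and map each to treatment through the randomisation schedule, as 11.2.1 already does for other endpoints. Show Table 1.14 and Listing 13 by treatment, with an exception to the by-sequence rule. Derive mg of GSK2646264 as 1% of the active-site weight, and define that as the actual dose in Tables 4.1 to 4.3.
- **Only a combined weight exists.** Label the exposure displays as total active plus placebo cream, delete the one-lesion footnote, and drop the actual-dose wording from the PK titles.

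The first route costs minor reprogramming of one table, one listing and one PK variable; the second is relabelling. Neither adds a patient procedure.

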11.3.3. Safety

ECG Parameters

RR Interval

- IF RR interval (msec) is not provided directly, then RR can be derived as :
 - [1] If QTcB is machine read & QTcF is not provided, then :

$$RR = \left[\left(\frac{QT}{QTcB} \right)^2 \right] * 1000$$

- [2] If QTcF is machine read and QTcB is not provided, then:

$$RR = \left[\left(\frac{QT}{QTcF} \right)^3 \right] * 1000$$

- If ECGs are manually read, the RR value preceding the measurement QT interval should be a collected value THEN do not derive.

Corrected QT Intervals

- When not entered directly in the eCRF, corrected QT intervals by Bazett's (QTcB) and Fredericia's (QTcF) formulas will be calculated, in msec, depending on the availability of other measurements.
- IF RR interval (msec) is provided then missing QTcB and/or QTcF will be derived as :

$$QTcB = \frac{QT}{\sqrt{\frac{RR}{1000}}} \qquad QTcF = \frac{QT}{\sqrt[3]{\frac{RR}{1000}}}$$

Laboratory Parameters

- If a laboratory value which is expected to have a numeric value for summary purposes, has a non-detectable level reported in the database, where the numeric value is missing, but typically a character value starting with '<x' or '>x' (or indicated as less than x or greater than x in the comment field) is present, the number of significant digits in the observed values will be used to determine how much to add or subtract in order to impute the corresponding numeric value.
 - Example 1: 2 Significant Digits = '< x ' becomes x - 0.01
 - Example 2: 1 Significant Digit = '> x' becomes x + 0.1
 - Example 3: 0 Significant Digits = '< x' becomes x - 1

Tolerability score

Tolerability will be assessed with the skin irritation scoring system for Part A and B of study, where the score consists of a numeric score according to the dermal response scoring i), and a letter according to the other effects scoring ii), as follows:

i) Dermal response scoring:

0 = no evidence of irritation

1 = minimal erythema, barely perceptible (pink)

2 = moderate erythema (definite redness), readily visible; minimal edema or minimal papular response

3 = strong erythema (intense redness), or erythema and papules

4 = definite edema

5 = erythema, edema, and papules

6 = vesicular eruption

7 = strong reaction spreading beyond test site

ii) Other effects:

Z = no other effect

A = slight glazed appearance

B = marked glazing

C = glazing with peeling and cracking

F = glazing with fissures

G = film of dried serous exudate covering all or part of the patch site

H = small petechial erosions and/or scabs

For each skin assessment, letter grade will be converted to numeric values as below:

A=0, Z=0, B=1, C=2, F=3, G=3, H=3.

A combined score for each subject will be calculated by adding all numeric and letter scores

The Skin Irritation Score for will be calculated for each subject at each timepoint and for each body part.

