
Group B will commence in parallel and recruit approximately 15 patients with a minimum of 2 active CLE lesions within the same anatomical area. At the day-5 to day -3 visit the two chosen lesions will be labelled based on size F (the larger) and G (the smaller). Pre-dose biopsies will be taken from both of the lesions (F+G) and an additional biopsy (H) from uninvolved skin from the same anatomical area will also be taken. The patients will be randomised 2-4 days later to allow for healing of the biopsies (F+G) and one lesion will then be treated with 1% GSK2646264 and the other with placebo once daily for 28 days. Biopsies will be obtained post-treatment from both treated CLE lesion (F+G). A completed patient will be defined as a patient who receives at least 25 days of study drug and completes the end of treatment biopsy (day 28) and assessment.

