ECG					
2.13.	Safety	EG1	Summary of ECG Findings (Group B-Natural Lesions)	Treatment columns will be replaced by one 'Part B' column	SAC
2.14.	Safety	CP_EG11	Summary of Maximum Emergent QTc Values by Category (Group B-Natural Lesions)	Treatment columns will be replaced by one 'Part B' column	SAC
2.15.	Safety	EG2	Summary of Change from Baseline in ECG Values by Visit (Group B-Natural Lesions)	Note: IDSL shell in development. Includes Baseline values. Treatment columns will be replaced by one 'Part B' column	SAC
2.16.	Safety	CP_EG12	Summary of Maximum Change from Baseline in QTc Values by Category (Group B-Natural Lesions)	Treatment columns will be replaced by one 'Part B' column	SAC
Vital Signs					
2.17.	Safety	VS1	Summary of Change from Baseline in Vital Signs by Visit (Group B-Natural Lesions)	Treatment column will not be displayed.	SAC
2.18.	Safety	VS3	Summary of Emergent Vital Signs Results Relative to Normal Range (Group B-Natural Lesions)	Treatment columns will be replaced by one 'Part B' column	SAC
Local Tolerability					
2.19.	Safety	SAFE_T1	Summary (Absolute and Change from Baseline) of Mean irritation score assessment – (Group B-Natural Lesions)		SAC
2.20.	Safety	SAFE_T2	Assessment of Maximum Dermal Reactions and Response (Group B-Natural Lesions)		SAC

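### The summed Skin Irritation Score in Table 2.19 can hide new other-effects irritation behind falling lupus erythema; change should be shown for each scale separately

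*SAP*

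**What the plan says.** SAP 11.3.3 grades local tolerability on two scales. The dermal response runs from 0 to 7 and its lower grades are defined mainly by redness, for example "3 = strong erythema (intense redness), or erythema and papules". The other-effects scale is a letter, with "H = small petechial erosions and/or scabs" as the last entry. Letters are converted to numbers ("A=0, Z=0, B=1, C=2, F=3, G=3, H=3") and then "A combined score for each subject will be calculated by adding all numeric and letter scores".

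Read alone, that sentence could mean adding across lesions. The next one says otherwise: "The Skin Irritation Score for will be calculated for each subject at each timepoint and for each body part". SAP 11.2.1 agrees: "Local tolerability, Efficacy and Pharmacodynamic endpoints are measured at a skin site level and therefore the following treatments will be used". I therefore take the score as one sum per lesion and timepoint.

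Table 2.19 is titled "Summary (Absolute and Change from Baseline) of Mean irritation score assessment", and its shell (SAFE_T1) is laid out by treatment and time. SAP Table 5 plans change from baseline for this score only. The row for the two separate scales has absolute displays only: Table 2.20 (shell SAFE_T2, maximum of each scale by treatment) and Listing 35 (shell SAFE_L1, both scales per visit).

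In Group B both treated lesions are active CLE and both are biopsied before dosing. Protocol 4.1 states: "The patients will be randomised 2-4 days later to allow for healing of the biopsies (F+G"). Protocol 7.1.3 schedules tolerability assessments from Day 1, pre-dose and up to an hour after dosing. The Group B baseline table in SAP 11.2.2.1 covers vital signs, laboratory samples, ECG, biopsies, RCLASI and plasma PK. It has no row for local tolerability.

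**The concern.** A sum is a fair summary of irritation when both parts can only rise from a clean baseline. These lesions do not start clean. Erythema and oedema appear in the dermal response scale and also in the modified RCLASI activity score (SAP 11.3.4), which the drug is meant to lower. The plan has no rule for telling lupus erythema from irritant erythema, or for grading a biopsy site. A lesion can therefore lose points for a reason unrelated to tolerability while gaining points from new peeling, fissures or exudate.

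At stake is the descriptive reading of local tolerability over time. Table 2.19 is where a reader would look for a drug-placebo difference in change from baseline, and a mean change near zero could be taken as no irritation.

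**Working it through.** **Inputs.** Dermal response d = 0 to 7. Letter value v: Z and A = 0, B = 1, C = 2, F, G and H = 3 (SAP 11.3.3). Score S = d + v, so it runs from 0 to 10. Change = post-dose S minus baseline S (SAP 11.2.2.2). I assume a Day 1 pre-dose baseline because the SAP states none. The plan gives no figure of its own to reproduce.

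**Falling erythema, worsening letter**
- 3Z to 0F: (0 + 3) - (3 + 0) = 0. Strong erythema clears, fissures appear, and the change is 0.
- 3Z to 1C: (1 + 2) - (3 + 0) = 0. New peeling and cracking is hidden in the same way.

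**Effect on the treatment comparison**
- Active 3Z to 0F = 0, placebo unchanged at 3Z = 0. Contrast 0, so the fissures do not show.
- Active 3Z to 0F = 0, placebo 3Z to 0Z = -3. Contrast +3, so they do show.
- The irritation is hidden only when erythema falls more on the active lesion than on the placebo lesion.

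**Healing biopsy scab (H to Z, -3)**
- 2H to 5Z: 5 - 5 = 0. A three-grade dermal rise disappears from that lesion's change.
- 2H to 7Z: 7 - 5 = +2. A rise of more than three grades still shows.
- There are 28 possible dermal increases. Rises of 1, 2 and 3 grades account for 7 + 6 + 5 = 18 of them, and those 18 give a change of 0 or less.
- Between treatments: active 2H to 5Z = 0 and placebo 2H to 2Z = -3. The contrast is +3, the full dermal rise.
- Arm-level illustration with 15 lesions and assumed counts, mean change = (3 x new reactions - 3 x healed scabs)/15. Five new three-grade reactions give +1.0 with no healing scabs, 0.0 with five and -1.0 with ten.

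**How many transitions can offset.** There are 8 x 7 = 56 grade combinations and 56 x 56 = 3,136 baseline/post-dose pairs.
- Letter pairs that worsen: 6 by one point, 5 by two and 6 by three, 17 in all.
- Dermal pairs that fall: 28 by at least one grade, 21 by at least two, 15 by at least three.
- Dermal falls and letter worsens: 28 x 17 = 476 pairs. Change of 0 or less: 6 x 28 + 5 x 21 + 6 x 15 = 363 (76%).
- Dermal worsens and letter improves: 28 x 17 = 476 pairs. Change of 0 or less: 6 x 7 + 5 x 13 + 6 x 18 = 215.
- Together: 363 + 215 = 578 of 952 opposite-direction pairs (61%), or 578 of the 1,984 pairs in which either scale worsens (29%).

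These counts weight every pair equally, including unlikely baselines such as vesicular eruption. They show that offsetting is built into the rule, not how often it would occur.

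**The case against.** The strongest reply is that the components are not lost. Table 2.20 tabulates the maximum on each scale by treatment, and Listing 35 gives both scales at each visit. In the 3Z to 0F example, Table 2.20 would show the F. Table 2.19 also reports absolute scores, which are not offset against baseline. The stated primary endpoint is laboratory tests, vital signs, ECG and adverse events. The irritation score is not named there, and the primary analysis is descriptive. The dose-limiting tolerability criterion in Protocol 5.4.1 uses the two scales separately, so no decision rule depends on the sum.

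Most of this stands and limits the importance of the point. Two gaps remain. The SAP does not say whether the Table 2.20 maximum excludes Day 1 pre-dose, so a baseline scab or baseline erythema could set it. And a listing is not a summary by treatment.

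A reader might infer that scab healing biases the drug-placebo comparison. The documents do not support that: both lesions are biopsied, and the contrast in the worked case is preserved. A grade of H on Day 1 is itself a supposition, since the interval before dosing exists for healing and nothing says how a punch site is graded.

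A reader might also infer that adding the letters is the whole problem. It is not. Falling lupus erythema can mask new irritant erythema within the dermal scale before any letter is added, and separating the scales leaves that in place.

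**Conclusion.** The point holds in a limited form. In the change-from-baseline half of Table 2.19, falling disease erythema can offset new other-effects irritation. If the drug reduces erythema more than placebo does, the drug-placebo comparison can miss it. Scab healing can distort each arm's mean change but largely drops out between treatments.

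This rests on three conditions: a Day 1 pre-dose baseline, which the SAP does not define; disease erythema being scored on the dermal scale, which nothing in the plan prevents; and an offset at least as large as the new reaction. The size in practice cannot be estimated from the documents.

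The stronger conclusion, that the score necessarily cancels irritation or biases the tolerability assessment as a whole towards no harm, is not supported. It would need the drug to clear erythema and irritate on the other scale at once, and it would ignore Table 2.20 and Listing 35. The change is worth making because it is cheap and recovers letter-scale worsening that the sum can hide.

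**What to change.** - **SAP 11.2.2.1:** add a local tolerability row naming the Day 1 pre-dose assessment as baseline.
- **SAP 11.3.3 and Table 2.19:** summarise change from baseline separately for the dermal response and the other-effects grade, by treatment and time. Add the number (%) of lesions that worsen from baseline on each scale. Keep the combined score as a supplementary row.
- **Table 2.20:** restrict the maxima to post-dose assessments. A scab still present after the first dose would still set the maximum at H, so read it beside the worsening counts.

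The cost is SAP wording and two extra blocks in an existing table. Both scales are already collected and listed, and no dose or stopping rule changes.

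The report should state two limits. Lupus erythema and irritant erythema remain confounded within the dermal scale. And because F, G and H all score 3, a lesion that starts at one of them cannot worsen on the converted other-effects scale.
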